5.3.9.4. Laboratory Parameters

A listing of all laboratory data will be provided (using SI units [International System of Units], when available) by treatment, patient and cycle. Normal reference ranges and percent of the result outside of range (result divided by lower limit if result is less than lower limit; result divided by higher limit if result is greater than higher limit) or change from baseline will also be included.

Relevant hematology and chemistry will be summarized according to CTCAE v4.0x grading. A listing of all hematology, chemistry (serum, special, ECG), AFP, E-cadherin, TGF- β +PF4, aPPT/PT/INR, Fibrotest and urine C-terminal telopeptides of Type 1 collagen will be provided by patient, cycle and cycle day.

5.3.9.5. Deaths

All deaths in this study, including the cause of death, will be listed by phase, treatment, patient and at the cycle when it occurred.

5.3.9.6. Hospitalizations and Blood Transfusions

A listing of patients who were hospitalized due to AE will be provided.

Patients that received blood transfusions, including the blood products received (that is packed red blood cells, platelets, fresh frozen plasma, or whole blood) will also be listed.

5.3.9.7. Vital Signs

Vital signs will be listed by patient, cycle and cycle day. This listing will include height, weight, respiratory rate, temperature, blood pressure and post-baseline ECOG performance status.

5.3.9.8. Electrocardiograms

Electrocardiogram (ECG) results will be listed for each patient by cycle, day within cycle, visit 801 and follow-up visits. This listing will include assessment of normality and clinical significance.

5.3.9.9. Echocardiograms

Echocardiograms (ECHO) results will be listed by treatment, patient and cycle and will include test date and left ventricular ejection fraction results.

5.3.9.10. Other Data

CT lot numbers of LY2157299 will be listed by treatment, patient and cycle.

5.3.10. Exploratory Analyses

Exploratory analyses/data mining will be carried out on imaging data, Fibrotest data, gene expression data, multi-analyte panel (MAP) of proteomics data and tumor-tissue data as appropriate, investigating links between these data and clinical and PD efficacy endpoints. Other TGF- β -signaling pathway biomarkers will also be included in this analysis.

After Amendment (a), both Child-Pugh Class A patients and Child-Pugh Class B7 patients are eligible and are being treated as 1 group given the similarity between these groups of patients, but additional analyses will look at the contribution of both classes to the clinical endpoints. In addition, as of Amendment (a), patients with liver transplant on maintenance immunosuppressive therapy are eligible, and possible differences in safety and efficacy endpoints between patients with and without liver transplant will be investigated.

After Amendment (c), first-line Child Pugh A patients are included in the study. Similar analyses to those conducted for patients in Parts A and B will be carried out for patients in Part C.

5.3.11. Clinical Registry Disclosure

The efficacy and safety analyses on the primary and secondary outcomes for CTR disclosure will be consistent with other document disclosure, for example CSR, manuscript and so forth. These results will be published on www.clinicaltrials.gov.

Analyses provided for the CTR requirements include an AE summary dataset and will be presented as follows:

- Both Serious Adverse Events and ‘Other’ Adverse Events will be summarized by treatment group and MedDRA preferred term.
- An adverse event is considered ‘Serious’ regardless of whether it is a treatment-emergent adverse event (TEAE).
- An AE is considered in the ‘Other’ category if it is both a TEAE and is not serious.
- For each Serious AE and ‘Other’ AE, for each event term and treatment group, the following are provided:
 - Number of patients at risk of an event
 - Number of participants who experiences each event term
 - Number of events experienced
- Consistent with www.ClinicalTrials.gov requirements, ‘Other’ AEs that occur in fewer than 5% of patients in every treatment group may not be included if a 5% threshold is chosen (5% is the minimum threshold).

Additional analyses will be performed for the purpose of fulfilling the CTR requirements.

6. References


7. SAP Attachments

SAP Attachment 1. FACT-Hep Scoring Guidelines (Version 4)

Instructions:*

1. Record answers in "item response" column. If missing, mark with an X
2. Perform reversals as indicated, and sum individual items to obtain a score.
3. Multiply the sum of the item scores by the number of items in the subscale, then divide by the number of items answered. This produces the subscale score.
4. Add subscale scores to derive total scores (TOI, FACT-G & FACT-Hep).
5. The higher the score the better the QOL.

Subscale	Item Code	Reverse item?		Item response	Item Score
PHYSICAL	GP1	4	-	_____	= _____
WELL-BEING (PWB)	GP2	4	-	_____	= _____
	GP3	4	-	_____	= _____
Score range: 0-28	GP4	4	-	_____	= _____
	GP5	4	-	_____	= _____
	GP6	4	-	_____	= _____
	GP7	4	-	_____	= _____

Sum individual item scores: _____

Multiply by 7: _____

Divide by number of items answered: _____ = **PWB subscale score**

SOCIAL/FAMILY	GS1	0	+	_____	= _____
WELL-BEING (SWB)	GS2	0	+	_____	= _____
	GS3	0	+	_____	= _____
Score range: 0-28	GS4	0	+	_____	= _____
	GS5	0	+	_____	= _____
	GS6	0	+	_____	= _____
	GS7	0	+	_____	= _____

Sum individual item scores: _____

Multiply by 7: _____

Divide by number of items answered: _____ = **SWB subscale score**

Subscale	Item Code	Reverse item?	Item response	Item Score	
EMOTIONAL WELL-BEING (EWB)	GE1	4 -	_____	= _____	
	GE2	0 +	_____	= _____	
	GE3	4 -	_____	= _____	
	GE4	4 -	_____	= _____	
	Score range: 0-24	GE5	4 -	_____	= _____
	GE6	4 -	_____	= _____	

Sum individual item scores: _____

Multiply by 6: _____

Divide by number of items answered: _____ = **EWB subscale score**

FUNCTIONAL WELL-BEING (FWB)	GF1	0 +	_____	= _____	
	GF2	0 +	_____	= _____	
	GF3	0 +	_____	= _____	
	GF4	0 +	_____	= _____	
	Score range: 0-28	GF5	0 +	_____	= _____
	GF6	0 +	_____	= _____	
	GF7	0 +	_____	= _____	

Sum individual item scores: _____

Multiply by 7: _____

Divide by number of items answered: _____ = **FWB subscale score**

HEPATOBIILIARY CANCER SUBSCALE (HCS)	C1	4 -	_____	= _____	
	C2	4 -	_____	= _____	
	C3	0 +	_____	= _____	
	C4	0 +	_____	= _____	
	C5	4 -	_____	= _____	
	Score range: 0-72	C6	0 +	_____	= _____
	Hep1	4 -	_____	= _____	
	Cns7	4 -	_____	= _____	
	Cx6	4 -	_____	= _____	
	HI7	4 -	_____	= _____	
	An7	0 +	_____	= _____	
	Hep2	4 -	_____	= _____	
	Hep3	4 -	_____	= _____	
	Hep4	4 -	_____	= _____	
	Hep5	4 -	_____	= _____	

Hep6	4	-	_____	=	_____
HN2	4	-	_____	=	_____
Hep8	4	-	_____	=	_____

Sum individual item scores: _____

Multiply by 18: _____

Divide by number of items answered: _____ = **HC Subscale score**

To derive a FACT-Hep Trial Outcome Index (TOI):

Score range: 1-128

$$\frac{\text{_____}}{\text{(PWB score)}} + \frac{\text{_____}}{\text{(FWB score)}} + \frac{\text{_____}}{\text{(HCS score)}} = \text{_____} = \text{**FACT-Hep TOI**}$$

To derive a FACT-G total score:

Score range: 1-108

$$\frac{\text{_____}}{\text{(PWB score)}} + \frac{\text{_____}}{\text{(SWB score)}} + \frac{\text{_____}}{\text{(EWB score)}} + \frac{\text{_____}}{\text{(FWB score)}} = \text{_____} = \text{**FACT-G Total score**}$$

To derive a FACT-Hep total score:

Score range: 1-180

$$\frac{\text{_____}}{\text{(PWB score)}} + \frac{\text{_____}}{\text{(SWB score)}} + \frac{\text{_____}}{\text{(EWB score)}} + \frac{\text{_____}}{\text{(FWB score)}} + \frac{\text{_____}}{\text{(HCS score)}} = \text{_____} = \text{**FACT-Hep Total score**}$$

SAP Attachment 2. NCCN/FACT Hepatobiliary Symptom Index-18 (FHSI-18) Scoring Guidelines (Version 4)

Instructions:*

1. Record answers in "item response" column. If missing, mark with an X
2. Perform reversals as indicated, and sum individual items to obtain a score.
3. Multiply the sum of the item scores by the number of items in the subscale, then divide by the number of items answered. This produces the symptom index score.
4. As with all FACIT questionnaires, a high score is good. Therefore, a score of "0" is a severely symptomatic patient and the highest possible score is an asymptomatic patient.

Scale	Item Code	Reverse item?		Item response	Item Score
FHSI-18	GP1	4	-	_____	= _____
Total	GP4	4	-	_____	= _____
	C2	4	-	_____	= _____
Score range: 0-72	HI7	4	-	_____	= _____
	CNS7	4	-	_____	= _____
	Hep2	4	-	_____	= _____
	GP6	4	-	_____	= _____
	Hep8	4	-	_____	= _____
	GP2	4	-	_____	= _____
	GP3	4	-	_____	= _____
	C6	0	+	_____	= _____
	GF5	0	+	_____	= _____
	GE6	4	-	_____	= _____
	GE1	4	-	_____	= _____
	GP5	4	-	_____	= _____
	AN7	0	+	_____	= _____
	GF3	0	+	_____	= _____
	GF7	0	+	_____	= _____

Sum individual item scores: _____

Multiply by 18: _____

Divide by number of items answered: _____ = **FHSI-18 score**

Subscale	Item Code	Reverse item?		Item response	Item Score
FHSI-DRS-P (Disease Related Symptoms-Physical)	GP1	4	-	_____	= _____
	GP4	4	-	_____	= _____
	C2	4	-	_____	= _____
	HI7	4	-	_____	= _____
	CNS7	4	-	_____	= _____
	Hep2	4	-	_____	= _____
	GP6	4	-	_____	= _____
	Hep8	4	-	_____	= _____
	GP2	4	-	_____	= _____
	GP3	4	-	_____	= _____
	C6	0	+	_____	= _____
GF5	0	+	_____	= _____	

Score range: 0-48

Sum individual item scores: _____

Multiply by 12: _____

Divide by number of items answered: _____ = **FHSI-DRS-P score**

FHSI-DRS-E (Disease Related Symptoms-Emotional)	GE6	4	-	_____	= _____
	GE1	4	-	_____	= _____

Score range: 0-8

Sum individual item scores: _____

Multiply by 2: _____

Divide by number of items answered: _____ = **FHSI-DRS-E score**

FHSI-TSE (Treatment Side Effects)	GP5	4	-	_____	= _____
--	-----	---	---	-------	---------

Score range: 0-4

Sum individual item scores: _____ = **FHSI-TSE score**

FHSI-F/WB (Function/ Well-Being)	An7	0	+	_____	= _____
	GF3	0	+	_____	= _____
	GF7	0	+	_____	= _____

Score range: 0-12

Sum individual item scores: _____

Multiply by 3: _____

Divide by number of items answered: _____ = **FHSI-F/WB score**

*For guidelines on handling missing data and scoring options, please refer to the Administration and Scoring Guidelines in the manual or on-line at www.facit.org.

SAP Attachment 3. List of Protocol Violations for H9H-MC-JBAK

Below is a list of potential protocol violations for this study. However, not all protocol violations listed here will be determined through programming. Additional source for the identifying the remaining protocol violations will be through investigator logs or note to file.

General:

- Any protocol inclusion/exclusion criteria violations:
 - Protocol Sections 8.1 and 8.2.
 - If patient with “entry criteria not met” is marked at Visit 0 but patient moves on to Visit 1.
- Treatment compliance (see Protocol Section 9.9):
 - Patients who are significantly noncompliant <80% or >120% of expected study drug taken in a visit interval.
 - Patients who are consistently out of the compliance range may be discontinued.
- Failure to receive annual approval of the investigator for the conduct of the study (monitor to check).

Study specific:

- Prohibited concomitant therapy (See Protocol Section 9.8):
 - other anti-cancer therapy (chemotherapy, target therapy, radiotherapy, except palliative radiation to non-target lesions);
 - immunotherapy;
 - hormonal cancer therapy;
 - experimental/investigational medication;
 - Rapamycin analogues;
 - Increased immunosuppressive therapy (Patients on maintenance immunosuppressive therapy after liver transplant are eligible);
 - At the discretion of the investigator, hormone-refractory prostate cancer patients who are stable on GnRH agonist therapy and breast cancer patients who are stable on antiestrogen therapy (for example, and aromatase inhibitor) may have that treatment continued while they are enrolled in this study.
- Visit outside visit intervals specified in protocol:
 - If treatment is held for ≥ 24 weeks due to toxicity and the patient is not discontinued from the study.
- If the patient requires two dose de-escalations during the course of the study and is then re-escalated to the higher dose level.

- Study drug not omitted in the case of the following AEs which are considered at least possibly related to study treatment:
 - ANC <0.5 10⁹/L for longer than 7 days, or ANC <1.0 10⁹/L with a single temperature of >101°F/38.3°C or a sustained temperature of >100.4°F/38°C for more than 1 hour or platelet count <25 10⁹/L.
 - CTCAE Grade 3 or 4 nonhematologic toxicity.
 - Study drug to be omitted from time of AE onset until adequate resolution (in the case of hematological toxicity, the definition of resolution is according to the investigator's opinion).
- Failure to perform PK collections.
 - Note: only collections “not done” are considered significant protocol violations.
- Failure to perform safety assessments.
- Failure to perform safety procedures or missing safety measurements per requirements in Study Schedule (Attachment JBAK.1 in Protocol).
 - Hematology/chemistry;
 - Chest CT/MRI 6 monthly;
 - ECGs;
 - ECHOs.
 - Note: only collections “not done” are considered significant protocol violations.
- Failure to perform efficacy procedures or missing efficacy measurements.
 - Tumor measurements:
 - Radiological Tumor Assessments (both baseline, post-baseline and post-baseline discontinuation from LY2157299 if applicable).
 - Palpable/visible (as applicable).
 - Note: only collections “not done” are considered significant protocol violations.
- Other protocol violations that result in study discontinuation as recorded on the CRF discontinuations page.
- Discontinuation criteria met but patient not removed from study (see Protocol Section 8.3.1)
 - If moderate or severe heart valve toxicities are observed, documented by echocardiography with Doppler and patient is not removed from study.

Leo Document ID = 83b1e165-b373-4665-af79-b5434c31bf66

Approver: PPD

Approval Date & Time: 11-Oct-2013 20:14:48 GMT

Signature meaning: Approved

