One cycle is defined as 28 days (a minimum of 26 days and a maximum of 31 days). The treatment period for LY2157299 must be a minimum of 10 days and a maximum of 14 days (for Parts A, B, C and D) and 21 days (for Part E); the “off-treatment” period can vary to ensure an overall cycle length of 26 to 31 days). In extenuating circumstances, the “on study drug” window for LY2157299 is allowable from Day 10 to Day 14. (In Part C and D safety lead-in Cycle 1, patients must have received 14 days of LY2157299 treatment). For Part E Cycle 1, all patients must receive 21 days of treatment, followed by 7 days off treatment. If patients are not evaluable for DLT assessment and/or PK in Cycle 1 of Part C or Part D safety lead-in, or Cycle 1 Part E, the patients will be replaced.

Per patient, the screening period is no more than 4 weeks or 28 days before the first dose of LY2157299; the planned treatment duration is 6 cycles or approximately 24 weeks, but patients may continue to receive study drug if they are still benefiting from treatment in the opinion of the investigator and Lilly physician. Follow-up visits will occur approximately 30 days after the last day of study treatment and subsequently approximately every 60 days (approximately 2 months [± 7 days]).

In case of the occurrence of severe toxicities in later cycles in patients treated with either LY2157299 monotherapy or LY2157299 in combination with ramucirumab or sorafenib, the sponsor will review and choose a lower dose or discontinue the patient, if necessary.

The final analysis for Parts A and B will be conducted after the study objectives for these 2 parts have been met. This is likely to be after approximately 30 deaths have occurred in Part B in order to have a reasonable estimate of overall survival in this patient group (AFP <1.5x ULN).

Part C will be considered complete and the final analysis initiated once 85% of events for survival analysis in the expanded cohort in Part C have occurred.

Part D will be considered complete and the final analysis initiated after the last patient has discontinued from study treatment and completed at least the 30-day follow-up visit [Visit 801].

Part E will be considered complete and the final analysis initiated after the last patient has discontinued from study treatment and completed at least the 30-day follow-up visit [Visit 801].

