9.1. Treatments Administered

The investigator or his/her designee is responsible for explaining the correct use of the investigational agent to the patient, verifying that instructions are followed properly, maintaining accurate records of study-drug dispensing and collection, and returning or destroying all unused medication to Lilly or its designee at the end of the study as requested.

Patients will be instructed to contact the investigator as soon as possible if he or she has a complaint or problem with the study drug so that the situation can be assessed.

Patients will keep a study diary to document that they are taking LY2157299 (Parts C, D and E) and sorafenib (Part C only) correctly.

A treatment delay at the start of a cycle (Day 1) of no more than 3 days, because of holidays, weekends, inclement weather, or other justifiable events, will be permitted and not counted as a protocol violation.

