9.5. Dose Adjustments

9.5.1. LY2157299

If a patient experiences any of the following events that are considered possibly related to LY2157299, LY2157299 will be omitted until the event resolves:

- ANC $<0.5 \times 10^9/L$ for longer than 7 days, or ANC $<1.0 \times 10^9/L$ with a single temperature of $>101^\circ F/38.3^\circ C$ or a sustained temperature of $>100.4^\circ F/38^\circ C$ for more than 1 hour or platelet count $<25 \times 10^9/L$
- CTCAE Grade 3 or 4 nonhematologic toxicity

Nonhematological toxicity must resolve to CTCAE Grade 0, 1, or baseline (with the exception of alopecia, fatigue, skin rash, nausea, vomiting, constipation, or diarrhea that can be controlled with treatment).

Hematologic toxicity must resolve to a level that, in the opinion of the investigator, is reasonable to allow for continuation of treatment.

If dosing is delayed for more than 2 weeks, the patient should be withdrawn from the study.

For Parts A and B, patients who do recover within the 2-week time frame may have the dose reduced to 160 mg for 300-mg dose arm and to 100 mg for 160-mg dose arm.

For Parts C and D: in case of a dose delay of LY2157299, patients can continue sorafenib or ramucirumab treatment (at investigator discretion).

For Part E, patients who do recover within the 2-week time frame may have the dose reduced to 160 mg or their schedule altered after discussion between the investigator and Lilly CRP.

No patient will have his/her dose reduced more than once. Re-escalation to the previous dose is acceptable in the absence of continuing or cardiac toxicities. If subsequent dose reduction is required after re-escalation, the patient must be maintained at the reduced dose level for all remaining cycles.

If moderate or severe heart valve toxicities are observed, the patient must immediately be discontinued from the treatment (for definitions see [Attachment 12](#), including references on the echocardiographic assessment based on the Guidelines of the American and European Societies of Cardiac Echocardiography). Exceptions to this rule must be approved by the ERBs.

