Baseline	
For change from baseline analysis, baseline value is defined as the last reported measure on or before the first dose date. For change from baseline within a cycle, the measure prior to the first dose if that cycle is baseline.

Entered	Patients who have signed the informed consent document directly.
Randomized	Patients who have been assigned to study treatment and have not received any study treatment (LY2157299).
Screen failures	Patients who have signed informed consent, do not meet eligibility criteria and are not randomized.
Enrolled, Patients on therapy	Patients who have been assigned to study treatment and have received at least 1 dose of study treatment (LY2157299).

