5.3.5. Patient Disposition

All patient discontinuation from study treatment and study will be documented, and the extent of each patient's participation in the study will be reported. Reason for their discontinuation from both study treatment and study will be listed and summarized by pre-determined categories. The planned treatment duration is 6 cycles, but patients may continue to receive study drug if they are still benefiting from treatment in the opinion of the investigator and Lilly physician. If known, unique reason for discontinuation will also be listed. If reason for discontinuation is due to AE or death, the associated AE or cause of death will be reported.

A listing of patients with identified protocol violations, including patients who did not meet inclusion/exclusion criteria, did not sign informed consent document at visit 0 and who discontinued due protocol violations, will be provided. See SAP attachment 3 for a list of potential protocol violations.

All enrolled patients will be accounted for in the summary of disposition. The number of patients who do not qualify for analysis, who die, or who discontinue before treatment begins, will be specified.

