5.3.9. Safety Analyses

5.3.9.1. Study Drug Exposure

The number of cycles completed per patient and dose intensity will be summarized using descriptive statistics (mean, median, minimum, and maximum).

Dose intensity for LY2157299 is derived according to the following formula:

- Planned cumulative dose (mg):

$$PLC_i = \text{number of cycles} * \text{assigned dose per day} * 14$$

where 14 is the planned number of dosing days per cycle.

- Prescribed cumulative dose (mg):

PRC_i = sum of prescribed dose multiplied by the number of dosing days in that cycle over all cycles.

The actual dosing is collected on days 1, 12, 13, and 14 of cycle 1 and day 1 of cycle 2, which aligns with the PK sampling day. Any dose modifications collected during the treatment period will be considered in the calculation of prescribed cumulative dose. Additional and/or detailed considerations for deriving of prescribed cumulative dose will be included in the TFL requirements. For interim data cut, the number of cycles up to the last completed cycle for patients in active treatment will be considered for this calculation; for patients that has discontinued from treatment, the number of cycles up to the last cycle will be considered.

- Dose intensity in percent:

$$PDC_i = (PRC_i / PLC_i) * 100\%$$

For each patient, dose intensity for LY2157299 will be listed based on cumulative doses received during study. Note prescribed dose is the same assigned dose if there is no dose modification. Listings of dose assignment and dose information on LY2157299 will also be provided.

Cycle delays, dose reductions, and dose omissions of LY2157299, including reasons, will also be listed. If the reason for dose modification is due to AE, the associated AE will be provided. The number and percentage of patients with any dose modifications will be summarized for the entire treatment period as well as for each cycle.

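### One line of SAP Attachment 3 flags an unwithdrawn toxicity hold only at 24 weeks or more; Protocol 9.5.1 sets withdrawal at a dosing delay of more than 2 weeks

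*SAP*

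**What the plan says.** SAP 5.3.5 (Patient Disposition) promises a listing of identified protocol violations and directs the reader onward: "See SAP attachment 3 for a list of potential protocol violations". In Attachment 3, under the bullet on visits outside the permitted intervals, one line applies when treatment is held for at least 24 "weeks due to toxicity and the patient is not discontinued from the study".

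Protocol 9.5.1 governs LY2157299 dose adjustment. It names the related toxicities for which the drug is omitted until they resolve, and then sets the limit: "If dosing is delayed for more than 2 weeks, the patient should be withdrawn from the study". For Parts A, B and E, patients who recover inside the two weeks may continue at a reduced dose (in Part E, alternatively on an altered schedule).

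The protocol uses 24 weeks for something else. Section 7.1 states that "the planned treatment duration is 6 cycles or approximately 24 weeks".

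**The concern.** The Attachment 3 line and the 9.5.1 rule address the same event: LY2157299 is stopped for toxicity, dosing does not resume in time, and the patient is kept on study. The line appears to have been written to police that rule. The items that follow it in Attachment 3 cover dose reduction and re-escalation, the neutrophil and platelet limits, and Grade 3 or 4 nonhematologic toxicity, all of which track 9.5.1. Only the hold line carries a number that the protocol does not.

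At stake is whether the violation listing identifies patients who should have been withdrawn and were not. The nonclinical findings for this drug include vascular and valvular lesions, so adherence to a toxicity stopping rule is something a reader of the study report would reasonably want classified correctly. A programmer or monitor applying the line literally would pass over a patient held for, say, ten weeks.

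**Working it through.** No power, alpha or event figure is involved. The check sets the texts side by side and compares the thresholds.

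1. **Inputs.** SAP Attachment 3: hold of at least 24 weeks. Protocol 9.5.1: delay of more than 2 weeks. Protocol 7.1: 6 cycles of 28 days. Protocol 9.5.2, footnote to Table JBAK.7: 30 days for sorafenib.

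2. **Thresholds in days.** SAP: 24 × 7 = 168. Protocol: 2 × 7 = 14. Ratio: 168 / 14 = 12.

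3. **Scale.** Planned treatment is 6 × 28 = 168 days. The printed line is therefore met only by a hold as long as the entire planned treatment.

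4. **Range the line misses.** More than 14 and less than 168 days. This describes one line, not a gap of that size in Attachment 3 as a whole.

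5. **Other possible sources for 24 weeks.** The sorafenib limit is 30 days, with an exception for clinical benefit, so Part C does not explain it. Neither document states 24 weeks as a hold limit for any drug.

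6. **Hold versus delay.** The SAP speaks of treatment being held and 9.5.1 of dosing being delayed; on an intermittent schedule these differ. Suppose a patient on 14 days on and 14 days off stops for toxicity from Day 10 and restarts on time at the next Day 1. Days without drug: 28 − 10 + 1 = 19. Dosing days missed: 14 − 10 + 1 = 5. Delay to the next cycle: 0. Counting calendar days, 19 exceeds 14, yet the next cycle was not delayed. The ratio of 12 treats the two measures as one. Counted in days without drug, it is smaller: after a full 14-day course, a 2-week delay means 14 + 14 = 28 drug-free days, and 168 / 28 = 6. The conflict remains on either count, but the wording of the replacement matters.

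7. **Effect on estimates.** SAP 5.2 bases efficacy and safety on all enrolled patients with at least one dose and excludes no one for a violation. The change to estimates is nil.

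**The case against.** A reader might infer that Attachment 3 as a whole lets toxicity holds go unrecorded until 24 weeks. The documents do not support that. The parent bullet on visit intervals could catch a late cycle, since Protocol 9.1 excuses only this much: "A treatment delay at the start of a cycle (Day 1) of no more than 3 days". A further item covers discontinuation criteria that were met without the patient being removed. It cites Protocol 8.3.1, which lists unacceptable toxicity, and its example, heart valve toxicity, is itself a stop found in 9.5.1. The attachment describes its contents as potential violations and says that "not all protocol violations listed here will be determined through programming", leaving the rest to investigator logs or notes to file. SAP 5.3.9.1 adds: "Cycle delays, dose reductions, and dose omissions of LY2157299, including reasons, will also be listed". All of this stands and limits the point to one line. None of these routes corrects that line, and the dose listing does not class a delay as a violation.

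Two points concern the evidence. The SAP is aligned with Amendment (c) and the protocol is Amendment (e). The 2-week sentence appears in the Amendment (e) change log and does not look like a new insertion, but change marks are not reliably preserved in the text available and the Amendment (c) wording is not. That the rule applied when this SAP was written is likely, but inferred. Also, 24 may be a slip for 2 or for 2–4. If the slip is in the SAP, the same correction is needed; if it arose only in converting the file to text, the point falls. A look at the source file settles it.

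Finally, the line says only treatment, and Protocol 7.1.1 counts sorafenib as part of study treatment in Part C. SAP 5.3.3 attaches the drug name LY2157299 to study treatment, and the neighbouring items follow 9.5.1, so LY2157299 is the better reading. It is still a reading, and the replacement should name the drug.

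**Conclusion.** The inconsistency is real as printed and small in consequence. One line of Attachment 3 uses a 24-week threshold where Protocol 9.5.1 uses more than 2 weeks, and it would not flag delays between those limits as failures to withdraw.

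A reader might go further and conclude that the SAP permits a 24-week hold, or that the trial's results are affected. Neither follows. Attachment 3 classifies departures and does not alter the dosing rule, and the analysis sets do not depend on violation status. Nor can it be said that any patient was misclassified, since no hold durations are given.

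The conclusion assumes that 24 is what the SAP source file prints, that treatment in this line means LY2157299, and that the 2-week rule was already in force under Amendment (c). Protocol 12.2.8 plans later SAP versions for Parts D and E. They are not among the documents, so a later correction cannot be ruled out. This is a low-priority correction.

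**What to change.** Replace the line with: *LY2157299 dosing delayed for more than 2 weeks (beyond the scheduled off-treatment period) due to toxicity and the patient is not withdrawn (Protocol 9.5.1).*

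Use delayed rather than held, so that the planned off days do not turn an on-time restart into a violation. Protocol 9.5.1 does not say when the delay starts to count; the parenthesis settles this for the listing. Leave sorafenib delays in Part C to the 30-day rule in Protocol 9.5.2, which has its own exception for clinical benefit.

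The cost is one line of text, plus an edit to the listing program if this item is programmed. No new data are needed, because LY2157299 delays and their reasons are already to be listed. Before editing, check the SAP source file and any later SAP version.
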